9.2.1 Treatment Assignment Procedures

Randomization will occur at the site level (cluster randomized trial). Ten sites will be randomized to either the intervention arm or usual care arm using statistical software (SAS, SAS Institute, Cary, NC). Randomized will occur after all sites have agreed to participate and site-level regulatory approval has occurred. Randomization will be stratified by site using estimated sample size (<125 vs. ≥ 125 veteran organ transplant recipients). This will be done to ensure an approximate even distribution of patients across study arms.

9.3 Outcomes

The outcomes that are assessed for this proposal all relate to evaluating the impact of an intervention designed to improve medication safety within Veteran organ transplant recipients that receive immunosuppression through the VA system. This population represents a high-risk group that has a high incidence of medication errors, non-adherence and adverse drug events often leading to health care encounters, including ER visits and hospitalizations, which cause significant accrual of health care costs.

9.3.1 Primary outcome

The primary outcome for this study will include the overall rate of ER visits and hospitalizations, compared between the intervention and control groups. These encounters will be captured electronically throughout the 24-month study through the use of the CDW, stored in the VINCI environment. In addition, to ensure encounters are captured in a comprehensive manner, we will also link the VA CDW data to CMS (Medicare) claims data and capture non-VA ER and hospitalization encounters (after study completion). As most transplant patients are dual users and have Medicare

insurance benefits, this linkage will provide a more accurate assessment of these health care utilization.³ We expect ER visits and hospitalizations to significantly decrease within the intervention arm, towards the latter half (second 12-months) of the study due to a lag effect of the intervention on this outcome. This expectation is based on our previous research in this field and assessment of pharmacist interventions on medication safety and reduced adverse drug events requiring hospitalization. ER visits and hospitalizations will be assessed and compared as described in the statistical analysis plan. These will be defined based on encounter criteria within the CDW and CMS data: all-cause ER visits and all-cause hospitalizations leading to at least one overnight stay will be included as events.

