- Previous studies demonstrate that interdisciplinary quality improvement endeavors, which include the empowerment of pharmacists to implement initiatives aimed at improving medication use, can substantially improve medication safety in transplant recipients during the perioperative phase. This data demonstrated a 40% reduction in adverse drug events leading to hospitalization, 14% reduction in length of stay >3 days and 50% reduction in 14-day readmissions. Our follow-up study, which measured the impact of a pharmacist-led formal medication reconciliation initiative, demonstrated that, on average, 2.3 medication errors per

transplant recipient discharge were prevented (3.4 vs. 1.1, $p<0.001$, respectively); although, medication errors were still apparent in a significant number of discharges, establishing the need of pharmacist involvement in the ambulatory phase of care for these high-risk patients.^{16,17}

Medication Safety in Veteran Transplants:

- Veteran transplant recipients are embedded within highly complex inter-facility systems of care, such that medication safety monitoring and care coordination in the ambulatory care setting is often fragmented and suboptimal. Our previous research has demonstrated that nearly two-thirds of Veteran transplant recipients are dual-users; with 62% having multiple providers managing the same conditions. This leads to a significant number of duplications and omissions in care. Medication discrepancies between systems are nearly universal as well. Thus, provider and system-level issues represent substantial reinforcing and enabling factors driving medication safety events in Veteran transplant recipients.³

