4.1 Inclusion Criteria (require both to be included)

- Veteran organ transplant recipients will be identified using ICD-9/10 codes from the VA electronic health record (CPRS). Patients must have an active code stating they are a recipient of an organ transplant. The following codes will be utilized:
 - ICD-9 codes: V42.0, V42.1, V42.6, V42.7, V42.83, V42.84, 996.81, 996.82, 996.83, 996.84, 996.86, 52.80

OR

- ICD-10 codes: C80.2, T86.1, T86.10, T86.11, T86.12, T86.13, T86.19, T86.2, T86.20, T86.21, T86.22, T86.23, T86.290, T86.298, T86.3, T86.30, T86.31, T86.32, T86.33, T86.39, T86.4, T86.40, T86.41, T86.42, T86.43, T86.49, T86.810, T86.811, T86.812, T86.818, T86.819, T86.9, Z48.2, Z48.21, Z48.22, Z48.23, Z48.24, Z48.280, Z48.288, Z48.298, Z94.0, Z94.1, Z94.2, Z94.3, Z94.4, Z94.83

AND

- Actively receiving at least one anti-rejection medication dispensed by the VA site. These medications include tacrolimus, cyclosporine, azathioprine, mycophenolate, sirolimus, everolimus, and belatacept.

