7.1 Serious Adverse Events (SAEs)

The intervention for this trial does not involve the administration of medications or investigational agents, but rather supplemental pharmacist-led care provided in addition to usual care already delivered to veteran organ transplant recipients. Thus, the intervention is considered minimal risk research. As part of this study, SAEs will be monitored, compared between the intervention and usual care group and reported to the IOC and independent transplant nephrologist on a bi-annual basis.

SAEs are defined as hospitalizations, ED visits, graft loss and death. Hospitalizations and ED visits will be obtained from VA CDW data housed in the VINCI environment. Graft loss events will be obtained from SRTR data linked to the VA data, while death will be obtained from both SRTR and VA CDW data. Due to the minimal risk of this study intervention and the fact that the intervention does not involve the administration of investigational agents, adverse events, including abnormalities in laboratory values, new syndromes or diseases or new or worsening patient symptoms will not be monitored or reported as a part of this study. These will be monitored and addressed under normal usual care provided to the veteran at the study sites.

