8 INTERVENTION DISCONTINUATION

The intervention will be discontinued based on the recommendations of the IOC and/or the expert transplant nephrologist opinion. These decisions will be based on bi-annual reports provided by the study biostatistician that will report SAE rates compared between the intervention and usual care groups. Discontinuation will be recommended if the intervention demonstrates increased harm or potential harm to veterans at sites randomized to the intervention. This decision will be made based on clinically or statistically significant differences that are apparent in SAE rates between intervention and usual care sites. Worrisome trends will also be considered in the IOC decision.

The study sample size and power analyses were not designed to specifically conduct interim analyses for outcomes and factor in early termination due to substantial improvements or futility. Thus, only safety concerns will be used as criteria for early stoppage.

If a particular site discontinues the intervention or usual care, attempts will be made to replace the site if possible. However, if the site discontinues the study after considerable intervention time has elapsed, data collection for follow up outcomes will be locked at that time point and a replacement site will not be recruited.

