10 DATA COLLECTION AND QUALITY ASSURANCE

10.1 Data Collection and Management

There will two general types of data used for this proposal, which includes operational data used for the dashboard system and research data to assess the impact of the intervention on outcomes. Operational data for the dashboard will be captured through querying the national VA CDW operational database using the FRS environment and stored in VISN 7 space already approved and allocated for this project. These data elements include diagnoses, laboratory values, medication regimens, refill histories, provider types and health care encounters (hospitalizations, ER visits), gathered and queried on a daily basis. The pharmacists at intervention sites will access their site-specific dashboard information stored on the server through an end-user permission access link that will restrict which patients are visible to ensure appropriateness of access to the correct PHI.

For the research component of the proposal, data will be captured through the research CDW and housed within the VINCI environment. We will link the VA data to the SRTR registry and CMS claims data. The CDW will provide data to assess outcomes including hospitalizations, ER visits and costs, as well as mortality. CDW data will also be used to assess interventions by querying pharmacists' progress notes. The CMS data will provide non-VA health care utilization, including hospitalizations and ER visits, as well as non-VA cost estimates. The SRTR data will provide all baseline donor, recipient and transplant characteristics as well as clinical outcomes, including acute allograft rejection, graft loss and death. We will also capture pharmacist entered data, which will be their assessments of the dashboard system. We will deploy a web-based data entry system that the intervention pharmacists will use during the first year of the intervention to assess the dashboard functionality. Queries answered by intervention pharmacists will include the number of alerts received, how many were considered clinically relevant/actionable, time to conduct the intervention and general intervention types. This data will be captured through the use of the REDCap system.

After data is cleaned and completely ready for analysis, we will remove identifiers from the final datasets. This will minimize the risk of loss of confidentiality. All data will be stored on the VINCI system and only approved study personnel will have access to this data.

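### Non-VA encounters are seen only through Medicare claims, and not at all in the interim safety rates, yet the plan neither accounts for coverage nor labels the gap

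*Combined protocol and SAP*

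**What the plan says.** **Primary outcome.** Section 9.3.1 counts all-cause emergency visits and hospital stays of at least one night. VA encounters come from the VA data warehouse (CDW): "These encounters will be captured electronically throughout the 24-month study through the use of the CDW, stored in the VINCI environment". For care elsewhere, the team will "link the VA CDW data to CMS (Medicare) claims data and capture non-VA ER and hospitalization encounters (after study completion"). Section 10.1 gives CMS the same role: "The CMS data will provide non-VA health care utilization, including hospitalizations and ER visits, as well as non-VA cost estimates". No other source of non-VA encounters is named.

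**Who has Medicare.** The stated reason for the linkage begins "As most transplant patients are dual users and have Medicare", with no figure. Section 2.2 reports that "nearly two-thirds of Veteran transplant recipients are dual-users". Section 4.1 requires a transplant code and "Actively receiving at least one anti-rejection medication dispensed by the VA site"; it does not require Medicare. Section 4.2 has no exclusions.

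**Analysis.** Section 9.4 censors at death, graft loss or a move away from the study site. The listed covariates are sociodemographic, comorbidity, donor and transplant variables. None concerns insurance, dual use or prior utilization. Randomization is stratified by site size only (Section 9.2.1).

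**Safety comparison.** Section 7.1 states: "Hospitalizations and ED visits will be obtained from VA CDW data housed in the VINCI environment". Graft loss comes from SRTR, and death from SRTR and the CDW. The IOC reviews these rates by arm bi-annually. On discontinuation, Section 8 says: "This decision will be made based on clinically or statistically significant differences that are apparent in SAE rates between intervention and usual care sites". Section 11.4 repeats this.

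**The concern.** An encounter that nobody can see is stored as zero, not as missing. The missing-data methods in Section 9.4 (mixed models under missing at random, multiple imputation) therefore have nothing to act on. Patients without Medicare claims stay in the denominator with a lower observed rate for the same true rate. If the arms differ in Medicare mix, the observed rate ratio departs from the true one, and the planned models include no variable that could absorb the difference.

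The interim comparison has a narrower view. The plan links CMS data because VA data alone miss encounters, but the rates shown to those who may recommend discontinuation rest on VA data alone and carry no label saying so. A move of visits from non-VA to VA hospitals would look like extra events even if total use were unchanged.

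**Working it through.** **1. The plan's own figures.** The documents give no Medicare coverage and no non-VA share of encounters, so there is no capture figure to reproduce. The useful yardstick is the 25% target in Section 9.2. With a rate of 1.269 per year (0.952 after a 25% reduction), 2 years, ICC 0.05 and 135 patients per site (1,350/10), the design effect is 1 + 134 × 0.05 = 7.7, and

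n per arm = (1.960 + 0.842)² × (1/1.269 + 1/0.952) / (2 × ln(0.75)²) × 7.7 = 87.2 × 7.7 ≈ 671.

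The total is 1,343, against 1,350 stated, so the sample size is not in dispute. The implied standard error of the log rate ratio is 0.288/2.802 = 0.103.

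**2. Medicare mix in the final analysis, no true effect.** Let f be the non-VA share of encounters and q the share of non-VA encounters with a Medicare claim. The observed fraction of encounters is (1 − f) + f·q, and the observed rate ratio is that fraction in the intervention arm divided by the same in control. Both f and q are assumptions. The dual-use figure in Section 2.2 counts patients, not encounters, so it does not fix f. Using q as coverage also assumes that covered and uncovered patients have the same non-VA share.

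| f | q, lower arm vs higher arm | Intervention arm lower | Intervention arm higher |
|---|---|---|---|
| 0.2 | 0.60 vs 0.70 | 0.92/0.94 = 0.979 | 1.022 |
| 0.4 | 0.60 vs 0.70 | 0.84/0.88 = 0.955 | 1.048 |
| 0.2 | 0.55 vs 0.75 | 0.91/0.95 = 0.958 | 1.044 |
| 0.4 | 0.55 vs 0.75 | 0.82/0.90 = 0.911 | 1.098 |

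Equal coverage gives exactly 1. A 10-point gap at f = 0.4 moves the log ratio by about 0.046, a little under half of the planned standard error.

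**3. How large a chance gap could be.** With five equally weighted sites per arm and between-site SD s in coverage, the arm difference has SD s·√(2/5). For assumed s of 5, 10 and 15 points, the 95% range (±1.96 SD) is about ±6, ±12 and ±19 points. A 10-point gap is plausible. A 20-point gap lies just outside the range even at s = 15.

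**4. A shift of care into the VA, total encounters unchanged.** Suppose d of all encounters move from non-VA to VA in the intervention arm. The VA-only ratio is (1 − f + d)/(1 − f). The final-analysis ratio is [(1 − f + d) + (f − d)·q] / [(1 − f) + f·q], with q = 0.7 in both arms.

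| f | d | VA-only safety ratio | Final-analysis ratio |
|---|---|---|---|
| 0.2 | 0.05 | 0.85/0.80 = 1.06 | 0.955/0.94 = 1.02 |
| 0.2 | 0.10 | 0.90/0.80 = 1.13 | 0.970/0.94 = 1.03 |
| 0.4 | 0.05 | 0.65/0.60 = 1.08 | 0.895/0.88 = 1.02 |
| 0.4 | 0.10 | 0.70/0.60 = 1.17 | 0.910/0.88 = 1.03 |

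At q = 1 the final-analysis ratio is 1.00 throughout.

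**The case against.** **Randomization covers it.** A chance difference between sites adds variance and does not bias the estimate in expectation. Section 9.4 models clustering by site, and the sample size allows an ICC of 0.05. This is right, and it rules out the tempting reading that incomplete capture favours the intervention. What stands is that this noise comes from measurement and can be reduced: a baseline covariate can account for part of it, and the plan has none.

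**The extremes need extreme inputs.** A ratio of 0.91 or 1.10 needs a 20-point gap and a 40% non-VA share together. If patients without Medicare use less outside care, the effect shrinks. Both points stand. At a 10-point gap the range is 0.955 to 1.048.

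**The shift of care is conjecture.** No section says that the intervention changes where patients go in an emergency. Section 11.2 limits contact to the telephone, and the alert table in Section 5.1 triggers on encounters at discharge, after the event. The pilot described in Section 2.2 accepted documentation of non-VA care as a resolution. The pharmacist's navigator role makes a shift possible, no more.

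**Safety review is broader than encounters.** Graft loss and death also draw on SRTR, so the review is not blind to all outside events. Stopping has no mechanical threshold; the IOC and an independent nephrologist exercise judgement. The remaining problem is an unlabelled table.

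**The gap may be narrower.** The documents do not say whether the CDW holds outside care paid for by the VA. The Design and Outcomes synopsis promises adjustment for patient, provider and facility characteristics, and Section 4 mentions zip code. Neither names coverage.

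**Conclusion.** The point holds as one of incomplete ascertainment with two consequences.

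In the final analysis, Medicare mix can move the observed ratio either way, by roughly 0.91 to 1.10 under no true effect. This assumes a non-VA share of 20-40%, a coverage gap of 10-20 points, and the same non-VA share in covered and uncovered patients. It is added noise, which the site effects partly carry.

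In the interim safety comparison, a shift of 5-10 points of encounters into the VA would show as a 6-17% excess in the intervention arm with no change in total use. In the final analysis the same shift gives about 1.02-1.03 at 70% coverage.

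A reader might infer that a shift into the VA could pass for benefit. It cannot: in the intervention arm it can only look like harm or hide benefit. Nor do the documents show that such a shift occurs. All magnitudes rest on assumed inputs, because the plan supplies none.

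**What to change.** 1. In Section 9.4, add Medicare coverage at baseline (study start, or entry for patients who join later) to the adjusted model. Prespecify one sensitivity analysis of the primary outcome restricted to patients with observable Medicare claims at baseline, reported beside the all-patient result. Do not restrict on or adjust for coverage measured after randomization, because that could introduce selection.
2. In Sections 7.1 and 7.2, label the interim hospitalization and ED comparison as VA-only and show each arm's pre-study VA-only rate beside it. A change from an arm's own past level can then be read alongside the difference between arms. The discontinuation rule is unchanged.

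**Cost.** SAP wording, one extra analysis, and a pre-study encounter query. The plan already draws VA cost data for the 24 months before the study (Section 9.3.2). Baseline Medicare enrolment must be obtained with the planned CMS linkage. The restricted analysis will have fewer patients and be less precise. Design and sample size do not change. Written in before outcome data are compared, the analysis is prespecified; added later, it would be post hoc.

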9.3.2 Secondary outcomes

Secondary assessment will include a cost benefit analysis. Overall health care costs accrued during the 24-month study, as well as those accrued in the 24-months prior to study initiation will be analyzed and compared between the control and intervention groups. Cost data will be standardized using the VA Health Economics Resource Center (HERC) definitions, which normalizes regional differences in costs due to variation in cost of living indices. As with the primary outcome, we will also acquire and link CMS claims data to gain a comprehensive assessment of costs, including those that accrue from non-VA care (after study completion). Costs will also be sub-analyzed into three predominant categories: inpatient costs, outpatient costs and pharmacy costs, as described in the statistical analysis plan. To fully assess if the intervention is has a direct monetary benefit, we will measure costs of the intervention will include estimates of time and resources to implement the dashboard and train and support the intervention site pharmacists. Similar to primary outcome, we expect that as ER visits and hospitalizations decrease within the intervention arm, there will be a corresponding decrease in overall costs as well, predominantly driven by inpatient costs. We expect this decrease to occur during the second 12 months of the study period, as the intervention is likely to have a lag effect on this outcome as well.

Another secondary outcome is to assess the success of the dashboard systems expansions and utilization. To do so, we will evaluate the dashboard's functionality by measuring and reporting descriptive statistics for the alert numbers, alert relevance, time and the actions taken with regards to the alert and the intervention magnitude. We will measure and report the time effort needed to conduct the interventions by study site pharmacists. Using REDCap, we will build an electronic data capture system, which allows the intervention pharmacists to efficiently enter alert and intervention information through a web-based portal, which will be housed within the VINCI environment. This information will be captured during the first 12 months of the intervention period, which will provide ample data without overwhelming the clinical pharmacists throughout the 24-month study. These measures will allow us to ascertain if the expanded dashboard is meeting expectations, with regards to functionality and efficiency. These measures will be assessed by investigators at quarterly intervals. If there is strong evidence to suggest particular components of the dashboard are not providing clinically relevant alerts or if the ratio of alerts to actionable alerts is exceedingly high, then the investigational team may decide to modify this component of the system. Thus, these

process measures will serve to both assess the dashboard functionality and allow for modification to improve the efficiency of the intervention. The time assessment data will allow us to determine the amount of time and effort implementing this system requires, as it relates to embedding it into normal workflow processes. This information will be important if the dashboard is deemed effective and is disseminated for use to across the VA, as it will allow administrators to accurately assess the required pharmacist time needed for implementation. Finally, we will assess the type and magnitude of the interventions made using this dashboard to ensure study fidelity. The categorization and magnitude of these interventions will be assessed using the Overhage criteria, which is a well-established and validated method used in numerous studies, included several published by the investigators proposing this study.⁵² We will also assess the number of potential immunosuppression safety issues that occur and compare these between the two study arms. To do so, we will use the dashboard to provide monthly measurements of the following: percent of patients with missing laboratory assessments, percent of patients with alarming laboratory values without follow up scheduled, mean adherence to immunosuppression, based on refill timeliness and estimated using the PDC, percent of patients with a significant drug interaction without a immunosuppressant level and percent of patients with hospital discharge or ED visit without follow up scheduled. These will be measured in all patients and compared between the intervention and control groups at monthly intervals.

As an exploratory assessment, we will measure and compare graft survival and patient mortality between intervention and control sites. This study is not powered to determine if the intervention improves these clinical outcomes. However, it is well established that hospitalizations are a substantial risk factor for graft loss and patient death.⁵³ Thus, it is possible that this intervention may produce differences with regards to these clinical outcomes, even if the magnitude of the estimates does not produce statistically significant differences. We will also assess graft loss and mortality to ensure patient safety and that the intervention is not causing harm. These data elements (death and graft loss) will be captured through both the VA system (VINCI) and linking to the transplant registry (UNOS). The investigational team has experience with linking VA data to SRTR registry databases feels confident that this is feasible and will produce accurate measures of these important clinical outcomes.

